7.2.1. Treatment Period (Day 1 - Day 29 of each treatment cycle)

Prior to Infusion (D1)

- Physical examination
- Vital signs/temperature it is recommended to monitor the patient's vital signs continuously every four hours during the first 24 hours after start of treatment/dose step.
- Neurological examination and writing test
- Routine bloods, U/E, LFTs, LDH, Coagulations screen, FBC (aproximately 30mL of blood)
- Urinalysis
- Concomitant medication
- AE/SAE assessment
- CADD pump attachment

During Infusion (D2 to D22)

The following procedures and tests will be performed on D1 to D29 during blinatumomab infusion:

- Physical examination (D2, D3, D8, D15, D22)
- Vital signs/temperature (D2, D3, D8, D15, D22). On D2 and D3 vital signs should be measured at least twice a day
- Neurological examination and writing test (D2, D3, D8, D15, D22)
- Routine bloods, U/E, LFTs, LDH, Coagulations screen, FBC (D2, D3, D8, D15, D22) (aproximately 30mL of blood)
- Concomitant medication ()
- AE/SAE assessment ()
- CADD pump change on days 4, 8, 11, 15, 22 and 25

At the end of the infusion period of cycle two to four the procedures and tests of D29 of the first cycle will be repeated.

End of Infusion (D29)

The following procedures and tests will be performed on D29 (end of infusion):

- Physical examination
- Vital signs/temperature
- Neurological examination and writing test
- Bone marrow aspiration/biopsy
- Routine bloods, U/E, LFTs, LDH, Coagulations screen, FBC (aproximately 30mL of blood)
- Serum Immunoglobulins (IgG)
- Concomitant medication
- AE/SAE assessment

Infusion free Interval from Day 30 to Day 43 (applies to each treatment cycle)

After completion of the 4-week infusion period a 2-week infusion-free period will follow before a new cycle starts. During this time, the patient will not need to visit the study centre. The infusion free interval may be prolonged for up to seven more days, if deemed necessary. If the treatment will be continued, study day 43 of the previous cycle will be day 1 of the subsequent cycle.

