4.5. Schedule of events

	Screening (within 21							Cycl	es 1 to	4					90 days	2-Year Follow-	NACAL -I
	days prior to treatment)	Day 1*§	Day 2§	Day 3	Day 4	Day 8 (+/- 2d)	Day 11	Day 15 (+/- 2d)	Day 18	Day 22 (+/- 2d)	Day 25	Day 29 (+/- 2d)	Days 30-42 (+ 7d)	Unschedule d visit	after last treatment (+/- 5d)	up Period ^	Withdrawal visit
Informed consent	X																
Eligibility assessment	Х																
Medical history	Х																
Physical exam,vital signs and temperature	х	х	х	Х		Х		Х		Х		Х		Х	Х	Х	х
Neurological exam and writing test	Х	Х	Х	Х		Х		Х		Х		Х		Х	Х		Х
ECOG performance status	Х															Х	
ECG	Х														Х		Х
Urinalysis	Х	Х	Х	Х		Х		Х		Х		Х			Х	Х	Х
Pregnancy test (if applicable)	Х														Х		Х
Haematology and biochemistry	Х	Х	Х	Х		Х		Х		Х		Х		Х	Х	Х	Х
Virology (HIV, HBV, HCV)	Х																
Serum immunoglobulins	Х											Х			Х		Х

	' after last													2-Year Follow-	With drawal		
	days prior to treatment)	Day 1*§	Day 2§	Day 3	Day 4	Day 8 (+/- 2d)	Day 11	Day 15 (+/- 2d)	Day 18	Day 22 (+/- 2d)	Day 25	Day 29 (+/- 2d)	Days 30-42 (+ 7d)	Unschedule d visit	treatment (+/- 5d)	up Period	Withdrawal visit
Bone Marrow aspirate (+/- trephine)	Х											X ⁺				Х	
Response assessment												Х					
Blinatumomab infusion			Continuous infusion days 1 – 28 of each cycle Treatment break														
CADD pump attendance#		х			х	х	х	х	х	х	х	х					
Concomitant medications	Х		<< Ongoing assessment >>														
Adverse events			<< Ongoing assessment until 90 days after treatment discontinuation >>								X						
Supportive Care Requirements						<<	Ongoi	ng assessi	ment ur	ntil treatme	nt disco	ontinuation	>>				Х

NOTES:

Data on concomitant medications, adverse events and supportive care requirements may be collected during unscheduled visits

[figure not shown]
§ indicates inpatient visits. All other scheduled visits are outpatient visits.

*Clinical assessments and laboratory assessment performed within 3 days prior to the first dose of blinatumomab will not have to be repeated on day 1 cycle 1

^For patients who did not undergo allogeneic HSCT, Efficacy follow-up visits for assessment of molecular relapse and until haematological relapse will take place 3-monthly (calculated from cycle 1 day 1) within the first year and 6-monthly within the second year until completion of a 2-year period after treatment with blinatumomab. Telephone follow-up will be performed for patients who have undergone HSCT.

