5.4. Preparation

The final blinatumomab solution for infusion should be prepared in a clean, sterile environment using aseptic techniques at the study site's pharmacy, even if the patient is treated as an outpatient. The volume (dose) of blinatumomab is calculated based on the patient's weight. As all patients will be greater than 45kg,the dose is 28 mcg/day.

Blinatumomab lyophilized powder for solution, the stabiliser solution and the final solution for infusion are for single use only. Any remaining concentrate or final solution for infusion should be disposed of.

First, the lyophilized formulation of blinatumomab will be reconstituted with 3 mL sterile water for injection (sWFI). Then, it will be further diluted into a 0.9% sodium chloride solution (normal saline) intended for intravenous infusion in 250 mL infusion bags. The used water for injection and sodium chloride solution must be commercially available and marketed in the United Kingdom for the purpose of intravenous infusion, marked with the exact Pharmacopeia term. Since blinatumomab will be administered via continuous intravenous route, it needs to be stabilized at low concentrations and must be prevented from adsorbing to surfaces. Therefore, the normal saline bag must be conditioned by prior addition of a product-specific diluent (stabiliser solution), resulting in a final diluent concentration of 0.5 mM citrate, 25 mM lysine hydrochloride and 0.002% (w/v) polysorbate80. Detailed instructions regarding the reconstitution and dilution of blinatumomab as well as the preparation of the IV bag prior to administration will be provided to the respective pharmacy before the investigational product will be applied for the first time (refer to Pharmacy Manual).

Blinatumomab will be administered via a continuous ambulatory drug delivery (CADD) pump. Blinatumomab solution for infusion must be administered at ambient temperature and must not be kept at ambient temperature more than 96 hours.

For storage prior to administration, the prepared infusion solution must be kept at 2°C to 8°C. The total storage and administration time must not exceed 10 days

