5.6. Administration

Blinatumomab will be administered as a continuous intravenous (CIV) infusion at a constant flow rate rate as specified on the prescription, via a low protein binding infusion line with 0.2 micron inline filter using a CADD Ambulatory Infusion Pump. The infusion is for four weeks followed by a two-week infusion free interval, which may be prolonged for up to seven more days, if deemed necessary. There should be no planned interruptions in the infusion, e.g. for i.v. administration of other medication. Patients will be hospitalized during at least the first three days after start of infusion of the first treatment cycle and during at least the first two days after start of infusion of subsequent cycles. After interruption of treatment for more than 4 hours, the infusion should be restarted in the hospital, under supervision of the investigator. After interruptions for up to 4 hours, the infusion can be continued without specific measures.

The CADD infusion bags will be prepared as either 72 hour or 96 hour infusions, with the bags being changed twice a week. To account for weekends and bank holidays, this will occur on Tuesdays and Fridays. Each cycle should being on a Tuesday.

The infusion rate of the 250mL bag depends on the duration of the infusion:

- 72 hour infusions: Administer at a constant infusion rate of 3.33 mL/h over 72 hours, to achieve a final infusion volume of 240 mL for each subject. Any remaining infusion solution volume present in the infusion lines must be discarded.
- 96 hour infusions: Administer at a constant infusion rate of 2.5 mL/h over 96 hours, to achieve a final infusion volume of 240 mL for each subject. Any remaining infusion solution volume present in the infusion lines must be discarded.

Problems with the infusion bag, pump, or intravenous access should be rectified as soon as possible by contacting the Acute Oncology Service on [name]

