7.2. Treatment Period (Cycle 1 - 4)

Patients will be hospitalised during at least the first three days of the first cycle and during at least the first two days of each following cycle. Before starting the infusion of blinatumomab, the patient will be examined physically and blood samples for safety laboratory parameters will be taken. For starting the study treatment the laboratory results will not have to be awaited.

Following the start of the infusion AE/SAE and concomitant medication will be evaluated continuously throughout the whole study until the 90-day visit. After the 90-day visit, only (S)AEs potentially related to blinatumomab should be documented in the CRF (and reported to the sponsor, if applicable). In addition, only anti-leukemic concomitant medication and medication related to blinatumomab related (serious) adverse events should be documented in the CRF. The vital signs and the laboratory tests will be repeated on D2 and D3 and at each visit during the treatment period.

Replacement of infusion bags will be performed as described in the Operations Manual. CADD pump infusion bags will be changed twice a week. To account for weekends and bank holidays, this will be on Tuesdays and Fridays. Each treatment cycle should begin on a Tuesday.

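### The bag-change list in section 7.2.1 leaves out the day 18 attendance that the schedule of events and the twice-weekly rule imply, so that, read literally, 168 h pass between changes although bags last only 72 h or 96 h

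*Protocol*

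**What the plan says.** Five places in the protocol bear on when the infusion bag is changed.

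- **Section 7.2.1** gives an explicit day list within the procedures that apply to each treatment cycle: "CADD pump change on days 4, 8, 11, 15, 22 and 25".
- **Section 7.2** states the frequency, "CADD pump infusion bags will be changed twice a week", and the weekdays: "this will be on Tuesdays and Fridays. Each treatment cycle should begin on a Tuesday". The same paragraph refers the replacement procedure to an Operations Manual, which is not among the documents.
- **Section 5.6** fixes the bag types and repeats the frequency: "The CADD infusion bags will be prepared as either 72 hour or 96 hour infusions, with the bags being changed twice a week". For the longer bag it specifies "96 hour infusions: Administer at a constant infusion rate of 2.5 mL/h over 96 hours, to achieve a final infusion volume of 240 mL". The shorter bag runs at 3.33 mL/h over 72 h to the same 240 mL. The section also rules out planned breaks in the infusion and asks for a restart in hospital after an interruption of more than 4 h.
- **Section 5.4** says that the solution "must not be kept at ambient temperature more than 96 hours".
- **Section 4.5**, the schedule of events, has a day 18 column and a row headed "CADD pump attendance". Its footnote says that the row covers connection, the twice-weekly changes and disconnection.

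**The concern.** The 7.2.1 list goes straight from day 15 to day 22. Every other interval in it is three or four days; this one is seven. No bag described in section 5.6 lasts that long, and section 5.4 would not allow one at room temperature for that time.

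The list is the visit-by-visit instruction for a continuous infusion and applies to every cycle, including cycle 1, on which the primary endpoint rests. If attendances were booked from it alone, the pump would run dry in the third week. That would be a break built into the plan, which section 5.6 rules out, and one long enough to call for its in-hospital restart. Section 6.8 allows up to two further sites in stage II. Staff there would depend on the written text more than the team that prepared it.

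**Working it through.** **Inputs.** Day 1 is a Tuesday (5.6, 7.2). Connection is on day 1 and disconnection on day 29 (4.5 and its footnote). Bags last 72 h or 96 h, each delivering 240 mL from a 250 mL bag (5.6). The ambient limit is 96 h (5.4). The listed changes are days 4, 8, 11, 15, 22 and 25 (7.2.1).

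**Step 1: reproduce the plan's own bag durations.** With day 1 a Tuesday, the Tuesdays and Fridays up to day 29 are days 1, 4, 8, 11, 15, 18, 22, 25 and 29. Interval = (next day - day) x 24 h:

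72, 96, 72, 96, 72, 96, 72, 96 h; total 672 h = 28 x 24 h.

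Tuesday to Friday is always 72 h and Friday to Tuesday always 96 h, which are exactly the two bag types in 5.6. Volumes agree as well: 3.33 x 72 = 239.8 mL and 2.5 x 96 = 240 mL.

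**Step 2: compare with the schedule of events.** The pump row has nine marks. The Tuesday/Friday rule gives nine days. The 7.2.1 list plus days 1 and 29 gives 6 + 2 = 8. Nine marks fit only if day 18 is one of them.

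**Step 3: intervals under the 7.2.1 list.**

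| From | To | Hours |
|---|---|---|
| 1 | 4 | 72 |
| 4 | 8 | 96 |
| 8 | 11 | 72 |
| 11 | 15 | 96 |
| 15 | 22 | **168** |
| 22 | 25 | 72 |
| 25 | 29 | 96 |

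The total is again 672 h, but one interval is 168 h, or 168 / 96 = 1.75 times the longest bag and the ambient limit.

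**Step 4: what a bag hung on day 15 can cover.** At 2.5 mL/h, 168 h would need 2.5 x 168 = 420 mL, against 240 mL delivered.

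- 96 h bag: empty on day 19; gap 168 - 96 = 72 h, or 3/28 = 10.7% of infusion days.
- 72 h bag, the usual Tuesday-to-Friday one: empty on day 18; gap 168 - 72 = 96 h, or 4/28 = 14.3%.

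Running out the whole 250 mL would add only about 3 to 4 h (250 / 3.33 = 75 h; 250 / 2.5 = 100 h). Either gap is far above the 4 h at which 5.6 asks for an in-hospital restart.

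**Step 5: timing against the primary endpoint.** The gap would start on day 18 or 19 and end on day 22. The marrow is taken on day 29, so 29 - 22 = 7 days of resumed infusion would come between.

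**The case against.** The strongest reply is that the list is incomplete rather than contradictory. It does not say that changes happen only on those days, so a site that also changes the bag on day 18 satisfies every section. Section 7.2 gives the twice-weekly rule in the text just before the list and refers replacement to the Operations Manual. Stage I is at one site, and section 5.6 has bags made up only for 72 h or 96 h. Section 5.11 adds regular infusion-centre visits for bag changes and a pump that monitors delivery. A missing number is unlikely to override all of this.

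Much of that stands. It makes harm in practice unlikely and points to a slip. It does not make the list right as written: a reader who takes it as the schedule gets an interval that 5.4 and 5.6 cannot accommodate. The weekly study visits in 5.11 do not rescue it either, since a seven-day bag would still conflict with both of those sections.

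Three stronger inferences are tempting, and the documents do not support them.

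- *Exposure is lost just before the primary marrow.* On the protocol's own days the gap closes on day 22, a week earlier.
- *Patients would be infused with solution past its ambient limit.* At the stated rates the bag empties first. To last 168 h it would have to run at about 240 / 168 = 1.43 mL/h, a rate that the protocol does not contain.
- *About 11% of drug is expected to be lost.* That figure assumes a 96 h bag on a Tuesday, when the regular pattern uses the 72 h one. Both 10.7% and 14.3% describe literal compliance and are not forecasts.

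**Conclusion.** The inconsistency is real and confined to one line. Sections 4.5, 5.6 and 7.2 agree with one another, and the durations in 5.4 and 5.6 fit them; only the 7.2.1 list differs. Followed literally, it leaves 168 h between changes and an empty pump for 72 to 96 h, or 3 to 4 of 28 infusion days in each cycle so run. This assumes a Tuesday start, the bag types and rates in 5.6, and no attendance between days 15 and 22.

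The matter is drug administration, not statistics. The sample size, the two-stage decision rule and the primary endpoint's definition and timing are untouched. What the Operations Manual says is unknown, and it may already prevent the problem. The line should still be corrected, because it is an operative instruction and correction is cheap.

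**What to change.** Reconcile the day list in 7.2.1 with the schedule of events (4.5), the ambient limit (5.4), the bag durations and weekdays (5.6) and the twice-weekly rule (7.2), so that all give the same change days. Check the Operations Manual against the reconciled list. The clinical and pharmacy team should settle which days apply; this review does not propose them.

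The cost is one line of protocol text and one check of the manual, preferably before any stage II site opens. No analysis, sample size or decision boundary changes.

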7.2.2. D43/D1 of Subsequent Cycle

If the treatment will be continued with a further cycle, the patient will be hospitalised for two days and the following procedures and tests will be performed:

- Physical examination
- ECOG performance status
- Neurological examination and writing test
- Vital signs/temperature
- Routine bloods, U/E, LFTs, LDH, Coagulations screen, FBC (aproximately 30mL of blood)
- Urinalysis
- Concomitant medication
- AE/SAE assessment
- Confirmatory bone marrow aspiration in case of central MRD result shows that the previous sample was technically inadequate.

7.3. Follow-up Period

7.3.1. 90-day Safety Follow-up Visit

A Safety follow-up visit will be performed at 90 days after the end of infusion with blinatumomab. In case an allogeneic HSCT is planned following treatment with blinatumomab, the 90-day Safety Follow-Up Visit should be performed at the latest possible timepoint prior to the initiation of transplant conditioning, even if the 90 days have not elapsed. This visit will also be documented as End-of-Core-Study Visit and the following procedures and tests will be performed:

- Physical examination and ECOG performance status
- Neurological examination
- Writing test
- Vital signs/temperature
- 12-lead ECG
- Routine bloods, U/E, LFTs, LDH, Coagulations screen, FBC (aproximately 30mL of blood)
- Urinalysis
- Pregnancy test (in women of childbearing potential)
- Serum immunoglobulins (IgG)
- Concomitant medication
- AE/SAE assessment

7.3.2. 2-Year Efficacy Follow-up Period

For patients who did not undergo allogeneic HSCT, Efficacy follow-up visits for assessment of molecular relapse and until haematological relapse will take place 3-monthly (calculated from cycle 1 day 1) within the first year and 6-monthly within the second year until completion of a 2-year period after treatment with blinatumomab. The following procedures and tests will be performed:

- Physical examination and ECOG performance status
- Vital Signs/Temperature
- Bone marrow aspirate/biopsy
- Routine bloods, U/E, LFTs, LDH, Coagulations screen, FBC (aproximately 30mL of blood)
- Urinalysis
- Recording of anti-leukemic concomitant medication
- Recording of AE possibly related to blinatumomab

For patients who underwent allogeneic HSCT the investigator will contact the patients or his/her treating physician (e.g. via phone) to receive information concerning haematological relapse free and overall survival. Also, information concerning the conditioning regimen, donor type and 100d HSCT related mortality will be collected in the CRF. In addition to the routine collection of adverse events within the core study and until 90 days after last administration of study medication, investigators will report adverse events possibly related to blinatumomab thereafter.

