The standard approach for molecular relapse of AML with t(8;21) is intensive salvage chemotherapy^{1,2}, a commonly used regimen being FLAG-lda²¹. The FLAG-lda salvage chemotherapy regimen is delivered as an in-patient and results in prolonged cytopenias requiring a prolonged in-patient stay (median of 32 days in the NCRI AML17 trial). Critical care admission is required in ~10% of patients. Supportive care requirements are high and patients required a median of 10.4 units of blood, 12.9 units of platelets and 19.3 days of IV antibiotics in the AML17 trial. 60 day mortality in this trial was 6%²¹.

For AML with t(8;21) one or two course of salvage chemotherapy is routinely given to patients with molecular persistence or relapse, as these patients will inevitable progress to a full haematological relapse without intervention. MRD monitoring in the UK for both adults and children is provided by the Cancer Genetics Service at Guy's Hospital, London. Samples are analysed and results and clinical advice given in accordance with European LeukaemiaNet guidelines¹⁸.

For patients with molecular relapse, MRD continues to be monitored and is used to track response to salvage chemotherapy and inform timing of transplant and post-transplant intervention. The advantage of this approach is that treatment can be initiated well before a full relapse has occurred when the patient is well and has normal blood counts.

Current treatment for molecular relapse is identical to that for haematological relapse, this is due to the lack of other effective treatment options until now. The development of blinatumomab offers the potential to deliver effective therapy to patients with a molecular relapse and without the need for debilitating intensive in-patient salvage chemotherapy. This approach would offer dramatic improvements in patient experience, quality of life and resource use and provides a potential window of opportunity for outpatient-based therapy.

4. Trial Objectives and Design

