4.1. Trial Objectives

In this study we propose to evaluate the safety and efficacy of blinatumomab for up to 4 cycles of therapy in patients with confirmed molecular relapse of t(8;21) positive AML.

The primary objective is to evaluate the efficacy of blinatumomab to induce complete molecular remission (MRD negativity) in patients with molecular relapse or persistence of AML with t(8:21), after one cycle of treatment.

Secondary objectives:

- To evaluate overall survival in patients with molecular relapse or persistence of AML with t(8;21) translocation treated with blinatumomab
- To evaluate the effect of blinatumomab on duration of MRD negativity
- To evaluate the effect of blinatumomab on the kinetics of MRD
- To evaluate resource utilization
- To evaluate the incidence of patients experiencing a grade 3 or greater nonhaematological toxicity during the first cycle of treatment.

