4.3. Secondary endpoints

- Incidence of patients experiencing a grade 3 or greater non-haematological toxicity during the first cycle of treatment.
- Incidence of molecular complete remission at any time from trial entry (evaluated at end of trial)
- Molecular relapse free survival time (evaluated at end of trial)
- Overall survival time (evaluated at end of trial)
- Number of days of hospital admission at 1, 3 and 6 months from entry
- Number of days on intravenous antibiotics or antifungals at 1, 3 and 6 months
- Number of blood components infused at 1, 3 and 6 months

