8.1. Definitions for Treatment Response Evaluation

- Complete molecular response is achieved if there is no amplification of *RUNX1-RUNX1T1* fusion transcripts in a technically adequate sample obtained after the first cycle of treatment.
- Two weeks after the first post treatment bone marrow sample was obtained (which is expected to be identical with day 1 of the second cycle), another bone marrow aspiration has to be obtained in case the previous specimen was technically suboptimal and did not allow evaluation for molecular complete response.
- Molecular relapse is defined as re-appearance of *RUNX1-RUNX1T1* fusion transcripts on two consecutive samples with an increase in transcript expression of

- more than 1 log₁₀ in a patient who previously tested negative in at least two technically adequate samples
- Molecular progression is defined as an increase in disease-related transcript expression levels of more than 1 log₁₀ confirmed on a second consecutive sample.
- Haematological relapse is defined as unequivocal detection of > 5% leukaemia cells in bone marrow as measured by cytological, microscopic assessment, presence of circulating leukaemia blasts, or extramedullary leukaemia.

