10.2. Analysis

All patients who have received at least one dose of the trial treatment will be included in the per-protocol analysis. The primary endpoint will be described in numerical terms and as a percentage of all participants. An interim analysis will be performed after 7 patients have been treated, as outlined in section 10.1. Final analysis will be performed at the completion of the trial.

As there are no between-group comparison planned, significance testing is not required. Survival end-points will be assessed at the end of the study, and calculated using the Kaplan-Meier method. AEs and SAEs will be reported as incidences for each patient and each cycle of treatment. The best response attained by each participant throughout the trial will be used to determine the molecular complete remission rate.

There will be no data imputation for missing data in the primary endpoints. Deviations from the initial statistical plan will be described and justified in the report of the trial results.

11. Trial Management Group

Further details of the TMG will be provided in the next version of the protocol.

12. Direct Access to Source Data and Documents

The Investigator(s) will permit trial-related monitoring, audits, REC review, and regulatory inspections by providing the Sponsor(s), Regulators and REC direct access to source data and other documents (e.g. participants' case sheets, blood test reports, X-ray reports, histology reports etc.).

13. Ethics & Regulatory Approvals

The trial will be conducted in compliance with the principles of the Declaration of Helsinki (1996), the principles of GCP and in accordance with all applicable regulatory requirements including but not limited to the Research Governance Framework and the Medicines for Human Use (Clinical Trial) Regulations 2004, as amended in 2006 and any subsequent amendments.

This protocol and related documents will be submitted for review to Health Research Authority (HRA), Research Ethics Committee (REC), and to the Medicines and Healthcare products Regulatory Agency (MHRA) for Clinical Trial Authorisation.

The Chief Investigator will submit a final report at conclusion of the trial to the KHP-CTO (on behalf of the Sponsor) and the REC within the timelines defined in the Regulations. The KHP-CTO or delegate will upload the final report to EudraCT on behalf of the Sponsor

14. Quality Assurance

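### Molecular relapse-free survival and duration of MRD negativity are not measured consistently: no molecular follow-up is scheduled after HSCT, and relapse needs two earlier negative samples where response needs one

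*Protocol*

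**What the plan says.** Section 4.3 of the Protocol lists the endpoint as "Molecular relapse free survival time (evaluated at end of trial"), with no restriction to patients who are not transplanted. Section 4.1 adds a related objective: "To evaluate the effect of blinatumomab on duration of MRD negativity". On analysis, section 10.2 says: "Survival end-points will be assessed at the end of the study, and calculated using the Kaplan-Meier method".

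Follow-up depends on transplant. Section 7.3.2 states: "For patients who did not undergo allogeneic HSCT, Efficacy follow-up visits for assessment of molecular relapse and until haematological relapse will take place 3-monthly" in the first year, then 6-monthly in the second, with a marrow at each visit. After HSCT the investigator contacts the patient or treating physician "to receive information concerning haematological relapse free and overall survival", plus transplant details. The footnote to the schedule in section 4.5 agrees: "Telephone follow-up will be performed for patients who have undergone HSCT". Section 5.5 allows HSCT in place of further cycles once at least one cycle has been given.

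Section 8.1 counts a complete molecular response on a single technically adequate sample without amplification. It defines molecular relapse as transcripts reappearing on two consecutive samples with a rise of more than 1 log10, "in a patient who previously tested negative in at least two technically adequate samples". Molecular progression is defined separately, as a confirmed rise of more than 1 log10.

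**The concern.** A single Kaplan-Meier curve should count the same event in every patient. Here, loss of molecular response is actively looked for in one group, while the other group is asked only about haematological relapse and death. The background in section 3 explains that UK practice detects relapse at the molecular level before overt relapse, so in transplanted patients the event may be found late or missed.

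Separately, the state that starts a remission (one negative sample) is weaker than the state from which the protocol allows a molecular relapse (two negatives). Some responders who lose their response early fall between the two definitions, and whether they do depends on how they entered the trial.

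At stake is the reading of how durable the response to blinatumomab is, in a trial of at most 17 patients where a few misdated events can move the curve.

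**Working it through.** **The plan's own figure.** The protocol gives no numerical target for this endpoint. Its only design figure is the Simon rule in section 10.1: at least 4 of 7 to continue, at least 11 of 17 for success, with rates of 50% and 75%. By exact two-stage binomial calculation, the probability of success is 0.1494 at 50% (limit 0.15) and 0.8597 at 75% (target 0.85). The design reproduces and is not in question; 17 and 75% are used below only as inputs.

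**Marrows on treatment.** A cycle lasts 42 days (section 5.5) and the marrow is on day 29 (section 8.3). Cycle k is therefore sampled on day 29 + 42(k − 1): days 29, 71, 113 and 155. With the maximum 7-day extension of every interval, it is day 29 + 49(k − 1): days 29, 78, 127 and 176.
- The day-43 marrow is taken only if the day-29 sample was technically inadequate (sections 7.2.2 and 8.1), so it does not give a second negative.
- A responder continuing treatment therefore cannot have two scheduled on-trial negatives before about day 71.
- The safety visit, which is brought forward to before conditioning if HSCT is planned, lists no marrow (section 7.3.1). A patient transplanted after cycle 1 has one scheduled post-treatment marrow.

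**Definitions applied to each entry route (section 7.1.2).**
- *Molecular relapse:* the entry rule already requires two earlier adequate negatives, and section 8.1 does not restrict its two negatives to on-trial samples. Such a patient may meet the relapse definition after one on-trial negative.
- *Molecular progression or persistence:* entry does not require two earlier negatives. A patient without them who is negative on day 29 and positive at the next two marrows is a responder but does not meet the molecular relapse definition.
- *The separate progression definition:* it has no prior-negative condition and could cover this patient. The protocol does not say that it counts for this endpoint, and it gives no reference level for a 1 log10 rise from undetectable.

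**How many responders might lack scheduled molecular follow-up.** The protocol gives no expected HSCT share, so the share h is an assumption. Section 3 cites a relapse cohort in which 57% were transplanted and 74% reached second remission; 20% to 74% is used as the range.

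Responders at the target rate: 17 x 0.75 = 12.75. Without scheduled molecular follow-up: 12.75 x h.

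| HSCT share (assumed) | No scheduled molecular follow-up | Remaining |
|---|---|---|
| 20% | 2.55 (about 2.6) | 10.20 |
| 40% | 5.10 | 7.65 |
| 57% | 7.27 | 5.48 |
| 74% | 9.44 | 3.32 |

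At a 50% response rate there are 8.5 responders, and the same shares give 1.7, 3.4, 4.8 and 6.3 without scheduled molecular follow-up.

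**The case against.** The case on the other side is substantial and narrows the point.

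- *A reader might infer that the endpoint cannot be measured at all.* The documents do not support that. Non-transplanted patients have marrows at the end of each cycle and through two years, so those with two negatives are covered by the definition as written.
- *A reader might infer that molecular relapse after HSCT is never recorded.* That is also too strong. Section 8.3 has molecular tests outside the protocol entered in the CRF if they are done, section 3 says MRD informs post-transplant intervention, and section 16 names laboratory molecular data as source data. What stands is that nothing is scheduled after HSCT and the planned contact does not ask for molecular status, so capture is left to chance.
- *Which events count, and how HSCT is censored, may be set out in a SAP that is not shown.* This is fair, and their absence is not the complaint. The complaint concerns what the protocol does fix: who is sampled, what is asked after HSCT, and how molecular relapse is defined. A SAP can choose a censoring rule but cannot recover results that were not collected, and censoring at HSCT is likely to be informative.
- *The direction of bias is not certain.* Agreed: it depends on how the affected patients are analysed.
- *Multiplying 57% by all 17 patients would give about 10 without molecular follow-up.* That is the wrong base, because only responders can lose a response. The share also comes from a salvage-chemotherapy relapse cohort, whereas these patients are in haematological remission and are generally expected to receive four cycles. Transplanted patients also have their day-29 marrows before HSCT.

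**Conclusion.** The point holds in a limited form. Molecular relapse-free survival and duration of MRD negativity are not measured on the same footing in all patients, for two reasons: molecular status after HSCT is neither scheduled nor requested, and the relapse definition leaves out some single-negative responders depending on their entry route. If those patients are analysed as event-free, or only at haematological relapse, the duration of remission is overstated; that condition must be stated with the conclusion.

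At the 75% target response rate, the first problem would touch roughly 2.6 to 9.4 of 12.75 responders, for assumed HSCT shares of 20% to 74%. The number affected by the second problem cannot be derived, because the protocol gives no expected mix of entry routes or rate of early loss of response.

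Only secondary endpoints are concerned. The primary endpoint, the Simon design and overall survival are unaffected.

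**What to change.** 1. In section 8.1, add an event definition specific to this endpoint: the earliest of (a) reappearance of transcripts after complete molecular response, confirmed on two consecutive samples, with no requirement for two earlier negatives and dated at the first positive; (b) haematological or extramedullary relapse; (c) death. The entry criteria and treatment rules need not change.
2. In section 7.3.2, add to the post-HSCT contact the collection of dated routine RT-qPCR results. Section 3 supports this: "MRD monitoring in the UK for both adults and children is provided by the Cancer Genetics Service" at the trial's own hospital, so results from routine monitoring should already be held there.
3. Add a sensitivity analysis of molecular relapse-free survival censored at HSCT, reported beside the main curve and with the caveat that such censoring may be informative.

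The cost is an amendment to wording, one more item at the post-HSCT contact and some extraction of laboratory results; no additional marrow is needed. The estimated duration of remission may look shorter than under the present rules.
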